2 STUDY SYNOPSIS

Study Objective

The purpose of this research study is to evaluate the clinical outcomes of the use of low-energy segment removal with a micro-interventional irrigation/aspiration port (MICOR-304) to evacuate the lens prior to intraocular lens insertion in subjects undergoing routine cataract surgery.

Study Population

Only 1 eye per subject will be enrolled into the study. Up to 100 subjects (100 eyes) will be enrolled into the first phase of the study and an additional 200 subjects (200 eyes) will be enrolled in the second phase of the study, for a total of 300 subjects (300 eyes). Subjects will be enrolled in one of the two cohorts of this clinical investigation. For the first 100 eyes enrolled – up to 75 eyes may be enrolled in Cohort 1 and up to 75 eyes in Cohort 2. For the additional second phase of 200 eyes – up 150 eyes may be enrolled in Cohort 1 and up to 150 eyes in Cohort 2. Overall, for the 300-study eye investigation, there should be no more than 225 eyes in either Cohort 1 or 2.

Study Design

This is multicenter, multi-cohort, prospective clinical study designed to provide longitudinal, observational, non-comparative clinical outcome data for mechanical non-phacoemulsification lens extraction using low-energy segment removal with a micro-interventional irrigation/aspiration port (MICOR-304) to evacuate the lens prior to intraocular lens insertion.

Subjects will be stratified into two Cohorts. Cohort 1 is comprised of eyes with mild-to-moderate cataracts only (Grade 1 to 2). Cohort 2 is comprised of eyes with moderate to more dense cataracts only (Grade 2+ to 3+).

Inclusion Criteria

1. Able to understand study requirements, willing to follow study instructions and willing to return for required study follow-up visits.
2. Willing and able to understand and complete the informed consent document
3. Subjects with a cataract grade of 1 to 3+ and are scheduled to undergo cataract surgery
4. Subjects \geq 18 years of age

5. Clear intraocular media, other than cataract

Exclusion Criteria for both Cohorts

1. Polar cataracts
2. Zonular instability
3. Subjects who have been diagnosed with dry eye which has been untreated and or would affect postoperative visual acuity outcomes (i.e., if the subject has had dry eye treatments / devices and has, or is undergoing treatment and deemed to be stable, they would be an eligible study candidate).
4. Concurrent participation or participation in any clinical trial up to 30 days prior to preoperative visit.
5. Subjects that are pregnant, lactating or planning to become pregnant during the course of the study

Primary Endpoint

Efficacy: Total lens removal time and amount of irrigation solution fluid volume used during the surgical procedure.

- Total lens removal time is defined in two phases:
 - The beginning time starts when the surgeon enters into the eye with the MICOR-304 to start the lens removal process and completing when the surgeon finishes the nucleus lens removal with the MICOR-304 before changing over to irrigation and aspiration.
 - The second phase of lens removal time is the irrigation and aspiration stage for cortex removal which starts when the irrigation and aspiration tip enters the eye and completion time is when the cortex is removed.
- Total irrigation solution volume will be recorded using the indicators on the waste bag which will have labels that have pre-defined markers to indicate milliliters (ml) of volume of irrigation solution used for the surgical procedure.

Safety: Rate of occurrence of intraoperative and postoperative adverse events (AEs)

Secondary Endpoints

- UCVA on day 1
- BCVA on days 7, 30
- Change in corneal thickness from baseline through Day 30
- Rate of occurrence of intraoperative and postoperative adverse events (AE)
- Results of slit lamp and fundus examinations, which are not considered to be AEs

- Total procedure time: defined as the beginning time when the surgeon makes the first incision in the eye and completion time is when the eye speculum is removed at the end of the procedure.

Schedule of Visits

Screening visit, intraoperative visit, post-operative day 1, day 7, day 30.

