6. STUDY POPULATION

Individuals will be assessed for study eligibility based on the criteria presented below:

Inclusion Criteria

1. Able to understand study requirements, willing to follow study instructions and willing to return for required study follow-up visits
2. Willing and able to understand and complete the informed consent document
3. Subjects with a cataract grade of 1 to 3+ and are scheduled to undergo cataract surgery
4. Subjects \geq 18 years of age
5. Clear intraocular media, other than cataract

Exclusion Criteria for both Cohorts

1. Polar cataracts
2. Zonular instability
3. Subjects who have been diagnosed with dry eye which has been untreated and or would affect postoperative visual acuity outcomes (i.e., if the subject has had dry eye treatments / devices and has, or is undergoing treatment and deemed to be stable, they would be an eligible study).
4. Concurrent participation or participation in any clinical trial up to 30 days prior to preoperative visit
5. Subjects that are pregnant, lactating or planning to become pregnant during the course of the study

Primary Endpoints

Efficacy: Total lens removal time and amount of irrigation solution fluid volume used during the surgical procedure.

- Total lens removal time is defined in two phases:
 - The beginning time starts when the surgeon enters the eye with the MICOR-304 to start the lens removal process and completing when the surgeon finishes the nucleus lens removal with the MICOR-304 before changing over to irrigation and aspiration.
 - The second phase of lens removal time is the irrigation and aspiration stage for cortex removal which starts when the irrigation and aspiration tip enters the eye and completion time is when the cortex is removed.
- Total irrigation solution volume will be recorded using the indicators on the waste bag which will have labels that have pre-defined markers to indicate milliliters (ml) of volume of irrigation solution used for the surgical procedure.

Safety: Rate of occurrence of intraoperative and postoperative adverse events (AE)

Secondary Endpoints

- UCVA on day 1,7,30
- Change in corneal thickness from baseline through Day 30
- Rate of occurrence of intraoperative and postoperative adverse events (AE)
- Results of slit lamp and fundus examinations, which are not considered to be AEs

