All subjects enrolled will return for defined follow-up visits pre- and post-operatively. Data collected from each scheduled and unscheduled (or interim) exam will be recorded on a Case Report Form (CRF).

Subjects who become ineligible for study participation after enrollment will be exited from the study and the reason for exit will be documented on the Subject Screening Log and noted as a screen failure.

Pre-Operative/Screening Visit

This visit can occur 0 to 60 days prior to surgery. The following information will be captured for the study eye at this visit:

- Demographic data (gender, age, race / ethnicity)
- Ocular history / ocular medications
- Cohort selection 1 or 2
- Identification of study eye (OS or OD)
- Cataract type and grade
- Manifest refraction and best-corrected visual acuity (BCVA)
- Slit lamp biomicroscopy
- Dilated pupil size measurement
- Goldmann tonometry
- Dilated fundus examination and C:D ratio assessment
- Central corneal pachymetry
- Macular OCT (optional)

Intraoperative

The following information will be captured for the study eye during surgery:

- Total lens removal time
- Total volume of irrigation fluid used
- Anesthesia type
- Other surgical procedures performed
- Device failure / malfunction
- Method / device used for cataract pre-segmentation
- MICOR-304 model used
- Type of viscoelastic used
- Total procedure time
- Any intraoperative AEs (capsule tear, corneal haze, other)

1 DAY Postoperative

This visit must occur at postoperative days 1-2. The following information will be captured for the study eye at this visit:

- Ocular medications

- UCVA (pinhole)
- Slit lamp biomicroscopy
- Goldmann tonometry
- Central corneal pachymetry
- AE assessment
- Macular OCT (optional)

1 WEEK Postoperative

This visit must occur at postoperative days 5-10. The following information will be captured for the study eye at this visit:

- Ocular medications
- Manifest BCVA
- Slit lamp biomicroscopy
- Goldmann tonometry
- Central corneal pachymetry
- AE assessment
- Macular OCT (optional)

1 MONTH Postoperative

This visit must occur at postoperative days 21-35. The following information will be captured for the study eye at this visit:

- Ocular medications
- Manifest BCVA
- Slit lamp biomicroscopy
- Goldmann tonometry
- Central corneal pachymetry
- Dilated fundus examination and C:D ratio assessment
- AE assessment
- Macular OCT (optional)

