8 STATISTICAL METHODS

Analysis Plan

Primary and secondary endpoints will be analyzed with descriptive statistics. Point estimates and confidence intervals will be calculated for each outcome. 95% confidence intervals for lens removal time and irrigation fluid volume will be calculated based on a t distribution.

Frequency tabulations of safety outcomes will be made at the 1 week and 1-month follow-up evaluations.

Sample Size

The sample size for this study is based on the following:

For safety, the pooled sample of 100 eyes will have a greater than 90% chance of detecting one or more rare adverse events, i.e., those with an expected rate of occurrence of 2.5%.

We anticipate that for Cohort 1 (grades 1 – 2) the mean lens removal time will be approximately 5 minutes, with standard deviation of 1 minute, and for Cohort 2 (grades 2+) the mean lens removal time will be about 10 minutes, with standard deviation 2 minutes. Under

these assumptions a sample of 50 eyes will produce a confidence interval width of approximately 0.56 minutes for Cohort 1 and 1.14 minutes for Cohort 2.

For Irrigation Fluid Volume we anticipate a mean of 30ml with a standard deviation of approximately 5ml for both Cohorts. Under these assumptions, a sample of 50 eyes will produce a confidence interval width of approximately 2.8ml for each Cohort.

Adverse Events

The number of subjects reporting at least 1 AE of a given type will be summarized. AEs not listed that occur during the study will be added to the summary of AEs. Summaries will also be provided for AEs considered to be related to the device. Each AE will be summarized by incidence and percentage.

Central Corneal Pachymetry

Central corneal pachymetry data will be summarized with N, mean, standard deviation, minima, median, and maxima. A 95% confidence interval will be provided for the change and percentage change from baseline. Change between two consecutive visits will also be summarized.

Slit Lamp and Fundus Exam Findings

Slit lamp, and fundus examination findings at scheduled follow-up visits will be tabulated such that the number and percentage of subjects in each category will be summarized.

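### The BCVA endpoint is defined as a postoperative level only, although screening BCVA is collected, so the planned summary cannot separate eyes that lost vision from eyes that already saw poorly

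*Combined protocol and SAP*

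**What the plan says.** **Endpoint.** The secondary endpoints in the synopsis (Section 2) include "BCVA on days 7, 30". The next item is "Change in corneal thickness from baseline through Day 30", so the plan names a change where it intends one. The secondary endpoints in Section 6 differ: they give "UCVA on day 1,7,30" and do not list BCVA.

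**Measurement.** Section 7 and Appendix 1 schedule BCVA at screening, 1 week and 1 month. Appendix 1 specifies Snellen. Day 1 has a pinhole acuity only. No uncorrected acuity is scheduled at 1 week or 1 month, so the schedule agrees with the synopsis and not with Section 6.

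**Analysis.** Section 8 states that "Primary and secondary endpoints will be analyzed with descriptive statistics" and that "Point estimates and confidence intervals will be calculated for each outcome". For pachymetry it adds that "A 95% confidence interval will be provided for the change and percentage change from baseline". It has no acuity subsection, no change in BCVA and no definition of vision loss.

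**Eligibility.** Section 6 requires media clear apart from the cataract. It excludes polar cataract, zonular instability, and dry eye that is untreated or "would affect postoperative visual acuity outcomes". It says nothing about macular disease, optic nerve disease, glaucoma or amblyopia.

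**Adverse events.** Section 9 requires every ocular event in the study eye to be reported and treats sight-threatening events as serious. Loss of BCVA is not on its list of expected events, which is not exhaustive. Severity is graded by discomfort and daily activity.

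**The concern.** There is no control arm, so each eye's own screening value is the only internal reference for its acuity. A summary of day 7 and day 30 levels does not use it. Two eyes that both finish at 20/40 look the same, even if one began at 20/200 and the other at 20/25.

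This matters most in Cohort 1, which accepts Grade 1 cataract. Section 3 notes that surgery is now done at low levels of visual impairment and that this raises the emphasis on safety. Eyes that start with good vision have the most to lose, and a modest loss in them is easily hidden in a table of levels. What is at stake is how well the study can describe visual safety. The primary efficacy results do not depend on it.

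**Working it through.** **1. The plan's own figures.** None concerns BCVA. The stated figures reproduce:
- Chance of at least one event at 2.5% in 100 eyes: 1 − 0.975^100 = 92.0% (stated as above 90%).
- Interval widths at 50 eyes, 2 × t(0.975, 49) × SD/√50: 0.568 min, 1.137 min and 2.84 ml (stated as about 0.56, 1.14 and 2.8).

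**2. What a level hides.** With logMAR = log10(Snellen denominator/20):

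| Screening → 1 month | logMAR | Change | In a table of levels |
|---|---|---|---|
| 20/200 → 20/40 | 1.000 → 0.301 | −0.699 (gain) | 20/40 |
| 20/25 → 20/40 | 0.097 → 0.301 | +0.204 (loss) | 20/40 |
| 20/200 → 20/100 | 1.000 → 0.699 | −0.301 (gain) | 20/100 |

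The first two rows differ only in the paired change. The third shows the reverse. If that eye could have reached 20/20, the change calls it a gain, and only the level shows a poor result.

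**3. Case mix and the mean level (illustration; inputs assumed).** Let a share p of eyes have prior disease costing 0.3 logMAR, with a within-group SD of 0.15. The mean shifts by 0.3p. The overall SD is √(0.15² + p(1−p)·0.3²).
- p = 5%: shift 0.015; SD 0.164; half-width at 300 eyes 0.0186; ratio 0.81.
- p = 20%: shift 0.060; SD 0.192; half-width 0.0218; ratio 2.75.
- At 50 eyes, the size Section 8 uses per cohort, even SD 0.15 gives a half-width of 0.043 and ratios of 0.35 to 1.4.

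The shift is below one line (0.1 logMAR) throughout.

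**4. Level against paired loss (simulation; inputs assumed).** 400,000 eyes; potential acuity of mean 0.02 (SD 0.06) in healthy eyes and 0.40 (SD 0.15) in diseased eyes; cataract cost of about 0.25 (SD 0.12); true loss of 0.2 logMAR from screening in 2% of eyes.

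| Diseased share | Mean level | Worse than 0.3 logMAR | Of these, truly lost | Paired loss |
|---|---|---|---|---|
| 0% | 0.029 | 1.8% | 99.7% | 2.0% |
| 10% | 0.067 | 9.1% | 20.1% | 2.0% |
| 20% | 0.105 | 16.3% | 11.4% | 2.0% |
| 30% | 0.143 | 23.6% | 7.9% | 2.0% |

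Mean paired change stayed at −0.243. That stability is built in: prior disease cancels, cataract severity was not varied, and screening BCVA had no measurement error.

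**5. Cataract severity and the mean change (gains assumed).** Take mean gains of 0.15 logMAR in Cohort 1 and 0.40 in Cohort 2. The 225-eye cap lets either cohort hold 75 to 225 of 300 eyes.
- 225/75: (225 × 0.15 + 75 × 0.40)/300 = 0.2125.
- 75/225: (75 × 0.15 + 225 × 0.40)/300 = 0.3375.

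The swing is 0.125, so the pooled mean change also depends on case mix.

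**6. Precision of a loss count (exact 95% intervals).**
- 300 eyes: 0 losses, 0 to 1.2%; 3 losses, 0.2 to 2.9%; 6 losses, 0.7 to 4.3%.
- 100 eyes: 0 losses, 0 to 3.6%; 2 losses, 0.2 to 7.0%.
- By cohort with 0 losses, the upper limit 1 − 0.025^(1/n) is 4.8% at 75 eyes and 1.6% at 225.

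**The case against.** The strongest reply is that the planned level is not wrong. It catches the dense-cataract eye that improves but still ends poorly, which a paired change misses. The paired mean has its own case-mix problem: the 0.125 swing in step 5 is larger than the 0.06 shift in step 3. Both points stand. They show that level and change are complementary and that the loss count is the more useful addition.

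A second reply is that harm is already captured. The adverse event rate is the primary safety endpoint, and Section 9 lists corneal edema, cystoid macular edema, retinal detachment and endophthalmitis among the expected events. A reader might infer that visual harm would go unseen; the documents do not support that. The reply holds only in part, because no acuity threshold triggers a report and a two-line loss without a listed diagnosis could go unrecorded.

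Third, a reader might infer that the study cannot show which eyes lost vision. That is true of the endpoint as worded but not of the dataset, which will hold screening and follow-up values. The analysis could be run later, but a threshold chosen after the data are seen carries less weight.

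Last, diseased eyes are eligible by omission. Their number is unknown and may be small.

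**Conclusion.** The point holds as a gap in the endpoint definition and analysis. The BCVA endpoint uses the postoperative level alone, the baseline is collected, and the eligibility criteria leave in several causes of poor acuity. The planned summary therefore cannot separate lost vision from poor starting vision.

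The size cannot be fixed from the documents. The shift of 0.015 to 0.06 logMAR rests on assumed prevalence and assumed disease effect, and its ratio to the interval half-width also depends on the assumed SD and sample size. It would be too strong to say that case mix will move the reported mean by several half-widths. No BCVA target or comparator is stated, so no decision in the plan turns on that mean.

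The endpoint is secondary and descriptive; sample size, primary efficacy and the adverse event endpoint are unaffected. Appendix 2 is redacted. Its title covers examination methods, so it is unlikely to define a change analysis, but this cannot be checked. The change is worth making because it improves what the study can say about visual safety from data already planned.

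**What to change.** 1. Reconcile the acuity endpoints: the synopsis has UCVA at day 1 and BCVA at days 7 and 30; Section 6 has UCVA at days 1, 7 and 30 and no BCVA. Make both agree with Appendix 1.
2. Keep the postoperative BCVA level.
3. Add to Sections 2, 6 and 8, by cohort and pooled, the number and percentage of eyes with BCVA two or more lines worse than screening, at 1 week and at 1 month, with an exact 95% interval. Define a line in advance: 20/40 to 20/60 is log10(60/40) = 0.176 logMAR, below a 0.2 logMAR cut, but two printed lines on a chart with a 20/50 line.
4. Add the paired logMAR change from screening to each visit with a 95% interval, and state the Snellen conversion.
5. State how to read them: mean change depends on cataract severity, so read it by cohort. Cataract removal can mask harm in dense-cataract eyes, so read level and change together.

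The cost is wording in three sections and one more table, with no new visit or measurement. The downside is small: the by-cohort loss count will be imprecise if a cohort is near 75 eyes, and measurement error in Snellen acuity may push a few eyes over the threshold.

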3 INTRODUCTION AND RATIONALE

Background

[figure not shown]
Global estimates suggest that 94 million people are visually impaired due to cataract and, of these, 20 million are blind.¹ Because the incidence of cataracts increases with age, an increase in the elderly population will lead to a significant increase in cataract prevalence. Approximately 25% of people aged 65-69 years have cataracts, a proportion increasing to over 68% of those aged 80+ years.³

In 2014, nearly 23 million cataract surgeries were performed worldwide; of these, over 3.6 million procedures were performed each in the US and EU.⁴ Cataract extraction with intraocular lens (IOL) implantation is the most commonly performed surgical procedure in the world. The safety and effectiveness outcomes of modern-day cataract surgery are well described in the literature.⁶ Technological advances have transformed cataract surgery so that now over 99% are performed on an outpatient basis with excellent surgical outcomes.⁸

As cataract surgery has become minimally invasive and more procedural in nature, it has been performed much earlier in the course of disease and patients' lives. It is not uncommon to perform cataract surgery in the patient's 5th decade rather than their 70's even at very low levels of visual impairment. This early intervention has placed additional emphasis on safety and reduced ocular trauma during cataract surgery.

Current phacoemulsification approach to cataract extraction involves high-frequency thermogenic ultrasonic needle to fragment the lens and remove it from the anterior segment of the eye. This can be associated with significant ocular morbidity particularly in advanced cataracts because the phacoemulsification needle produces significant amount of energy and generates heat which is detrimental to the cornea and the endothelium.

Mechanical approaches to lens fragmentation and aspiration such as the MICOR-304 fragmentation and lens removal provide an alternative to phacoemulsification with no cavitation, no thermogenic energy in the eye which can eliminate the generation of heat inside the eye while at the same time maintaining the same minimally invasive surgical approach through a small clear-cornea 2.5 mm incision.

4 STUDY OBJECTIVES

The purpose of this research study is to characterize the clinical outcomes of mechanical and ultrasound-assisted lens fragmentation techniques in routine cataract surgery. The study will provide longitudinal, observational, non-comparative clinical outcomes data for mechanical lens fragmentation techniques.

5. STUDY DESIGN

This study protocol is a dual cohort, prospective, multi-center, interventional study whose goal is to evaluate the clinical and surgical outcomes of mechanical lens fragmentation techniques. The study is planned for up to 10 investigational sites. Only 1 eye per study subject will be enrolled into the study.

6. STUDY POPULATION

Individuals will be assessed for study eligibility based on the criteria presented below:

Inclusion Criteria

1. Able to understand study requirements, willing to follow study instructions and willing to return for required study follow-up visits
2. Willing and able to understand and complete the informed consent document
3. Subjects with a cataract grade of 1 to 3+ and are scheduled to undergo cataract surgery
4. Subjects \geq 18 years of age
5. Clear intraocular media, other than cataract

Exclusion Criteria for both Cohorts

1. Polar cataracts
2. Zonular instability
3. Subjects who have been diagnosed with dry eye which has been untreated and or would affect postoperative visual acuity outcomes (i.e., if the subject has had dry eye treatments / devices and has, or is undergoing treatment and deemed to be stable, they would be an eligible study).
4. Concurrent participation or participation in any clinical trial up to 30 days prior to preoperative visit
5. Subjects that are pregnant, lactating or planning to become pregnant during the course of the study

Primary Endpoints

Efficacy: Total lens removal time and amount of irrigation solution fluid volume used during the surgical procedure.

- Total lens removal time is defined in two phases:
 - The beginning time starts when the surgeon enters the eye with the MICOR-304 to start the lens removal process and completing when the surgeon finishes the nucleus lens removal with the MICOR-304 before changing over to irrigation and aspiration.
 - The second phase of lens removal time is the irrigation and aspiration stage for cortex removal which starts when the irrigation and aspiration tip enters the eye and completion time is when the cortex is removed.
- Total irrigation solution volume will be recorded using the indicators on the waste bag which will have labels that have pre-defined markers to indicate milliliters (ml) of volume of irrigation solution used for the surgical procedure.

Safety: Rate of occurrence of intraoperative and postoperative adverse events (AE)

Secondary Endpoints

- UCVA on day 1,7,30
- Change in corneal thickness from baseline through Day 30
- Rate of occurrence of intraoperative and postoperative adverse events (AE)
- Results of slit lamp and fundus examinations, which are not considered to be AEs
- Total procedure time is defined as the beginning time when the surgeon makes the first incision in the eye and completion time is when the eye speculum is removed at the end of the procedure

Schedule of Visits

Screening visit, intraoperative visit, post-operative day 1, day 7, day 30

